5.4. DEFINITION

Table 3 : Definitions

Term	Definition
Investigational Device (ID)	Perceval valve is a bioprosthetic heart valve made of bovine pericardium, stabilized in a buffered glutaraldehyde solution and assembled on a nitinol stent. The device is indicated for the replacement of a damaged or malfunctioning native heart valve in humans via traditional surgery.
Study Day Count	The day of implant is defined as study Day 1. Calculate the study day according to the following rules: If date < study Day 1 then study day = Date – study Day 1 If date > study Day 1 then study day = Date – study Day 1 +1
Baseline	Last preoperative assessment
Screening Failure	Screened patients who do not fulfill IE criteria OR patient who signed the IC but withdrawn from the study for termination reason is “Failure to meet randomization criteria”
Study completers	Patients who complete 5 year visit. The termination reason is “Completed the Study”
As-treated principle	Patients will be assigned to the treatment groups according to the device actually implanted to the subject.
As-randomized principle	Patients will be assigned to the treatment groups according to the randomization list independently from the actual implant to the device under investigation.

Term	Definition
Study phases	
 • Screening & enrolment • Operative evaluation • Hospital Discharge 
Assessments at:
 
 • 1 month (M1): 30 days \pm 7 days. The information (EQ5D) should be submitted to the site during the 1-3 months visit. • 1 to 3 months FU visit (M3): between 30 and 90 days • 1 year FU visit (Y1): 1 year (365 days) \pm 30 days after the day of the surgery • 2 years FU visit (Y2): 2 years (730 days) \pm 30 days after the day of the surgery • 3 years FU visit (Y3): 3 years (1095 days) \pm 30 days after the day of the surgery • 4 years FU visit (Y4): 4 years (1460 days) \pm 30 days months after the day of the surgery • 5 years FU visit (Y5): 5 years (1825 days) \pm 30 days after the day of the surgery

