13.1.2. Adverse Events Incidences

The incidence of AE is defined as the number of subjects with occurrence of this AE during the period of interest. The incidence rate (CIR for crude incidence rate) of an AE is defined as the number of subjects with occurrence of this AE during the period of interest divided by the total number of subjects n in the respective group (e.g., treatment group).

The incidence, incidence rate, the number of events and the percentage of events (related to the total number of events) will be summarized by AE term over the entire study post-implant period (from Day 1) and during the early and late phases (section 18.12). For the late events, the incidence rate will be calculated on the number of late patients only.

In addition, safety summaries will be done according to the following plan:

- Intraprocedural and periprocedural (within 72 hours) serious adverse events regardless of relationship with the device.

- All valve and procedure relevant (according to CEC adjudication) serious adverse event composite endpoints and their components as specified in VARC-2 guidelines (and reported in section 18.12):
 - Early safety at 30 days
 - Clinical efficacy after 30 days
 - Time related valve safety annually up to 5 years
- Serious device related (according to CEC adjudication) adverse events up to 5 years (from day 1 up to Day 1826)
- Postoperative site-reported unexpected serious adverse device effect (USADE)
- Site-reported relationship to procedure, device, drug/medication, or other Protocol Required Assessment (section 18.12)
- All late serious adverse events will be analyzed according to a constant hazard model: the linearized rates will be calculated as:
 - total number of late events divided by the total time under evaluation after 30 days (late patient-years).
 - number of patients with at least one late event divided by the total time under evaluation after 30 days (late patient-years).
- The incidence, incidence rate, the number of events and the percentage of Pacemaker (PM) implantation according to:
 - time of occurrence (overall, early, late and up to 1 year), and
 - relationship to device and procedure.

In addition, time-to-event methods (section 5.2) will be used to summarize the time to onset of the following events:

- deaths (overall, cardiovascular, and non-cardiovascular),
- explants and
- all main cardiovascular SAEs:
 - Bleeding,
 - SVD,
 - endocarditis,
 - valve thrombosis,
 - thromboembolic events,
 - stokes,

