MACCE @ n year (Yes/No)	
CEC adjudication of Serious Adverse Event (SAE), Valve re-intervention:
 
YES if at least one per CEC:
 
 - Death (Time to SAE <=n*365.25 days) - Myocardial infarction (Time to SAE <= n*365.25 days) per CEC - Stroke (Time to SAE <= n*365.25 days) per CEC - Reintervention (Time to SAE <= n*365.25 days) 
NO, otherwise

PM implant	
SAE FORM – TREATMENT
 
Yes if:
 
 - Was a pulse generator implanted? = YES - If yes, specify = Pacemaker 
NOTE: PM implant will be classified as intraoperative, early or late according to the date of PM implant (not the AE start date)

Derived variable	Derivation algorithm
Last exposure date	
Study Termination, Serious Adverse Event (SAE):
 
 1. For explant of investigational device: date of explant 2. For dead subjects: date of death 3. For alive and not explanted subjects: 
 - Date of termination - If there is no date of termination, the last available FU date (including discharge) or the last SAE date (occurrence date), whichever occurs later. - If there is no follow-up and no adverse events : date of surgery or date of randomization, whichever occurs later.
Last study date	
Study Termination, Serious Adverse Event (SAE):
 
 1. For dead subjects: date of death 2. For alive subjects: 
 - Date of termination - If there is no date of termination, the last available FU date (including discharge) or the last SAE date (occurrence date), whichever occurs later. 
If there is no follow-up and no adverse events : date of surgery or date of randomization, whichever occurs later.

Study length (days)	
Study termination, Subject Information:
 
Last study date – Enroll Date+1

Extent of exposure (days)	
Last exposure date-surgery date+1

Late patients	
Subjects with more than 30 FU days of exposure

Patient-years	
Cumulative Study length (days)/365.25

Derived variable	Derivation algorithm
Early patient-years	Cumulative Study length (days) up to 30 days/365.25
Late patient-years	Cumulative Study length (days) from 31st day/365.25. Subjects with less than 31 FU days do not contribute to the late patient-years

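### SAP Table 8 gives a living control patient with an explanted valve no last exposure date, which affects extent of exposure and the crude late incidence rate only

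*SAP*

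**What the plan says.** SAP 18.12 (Table 8) derives the last exposure date by three rules:

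1. "For explant of investigational device: date of explant".
2. "For dead subjects: date of death".
3. "For alive and not explanted subjects": the termination date or, failing that, the latest follow-up or SAE date, with a fallback to surgery or randomization.

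The SAP's definition of the investigational device (5.4, Table 3) begins "Perceval valve is a bioprosthetic heart valve made of bovine pericardium, stabilized in a buffered glutaraldehyde solution and assembled on a nitinol stent". The control valve is not part of it.

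Two derived variables depend on this date. Extent of exposure is "Last exposure date-surgery date+1". Late patients are "Subjects with more than 30 FU days of exposure". SAP 13.1.2 then states: "For the late events, the incidence rate will be calculated on the number of late patients only".

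A late SAE is defined differently. Table 8 requires only that the time from surgery to the SAE, counting the surgery date as day 1, exceed 30 days. It sets no condition on exposure. Protocol 18.1 requires explanted subjects to be followed at least to the one-year endpoint.

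**The concern.** There are two defects in the derivation rules.

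**A gap for controls.** A control patient who is alive after explant is not covered by rule 1 (wrong device), rule 2 (not dead) or rule 3 (explanted). That patient has no last exposure date, and so no extent of exposure and no late-patient status. The matching Perceval patient is covered by rule 1. Such controls can be expected: explanted subjects remain in follow-up, and SAP 13.1.2 plans a time-to-event summary of explants.

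**A numerator and denominator that do not match.** Wherever exposure stops at explant, a patient explanted by day 30 is not a late patient. If that patient is still followed and has an SAE after day 30, the event counts as late while the patient is missing from the denominator.

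At stake is whether extent of exposure and the crude late incidence rate are built alike in the two arms, and whether the rate is a proper proportion. Sponsor personnel run the primary and follow-up analyses of this open-label trial, so the comparator's exposure rule should not be left to a programmer's choice.

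**Working it through.** The documents give no figure to reproduce here. The check applies the rules literally and then scales the effect.

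**Step 1: apply the three rules.** The example patient is enrolled on the day of surgery and followed to, or dies at, 400 days after surgery. Exposure is the last exposure date minus the surgery date, plus 1.

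| Valve | Explant (days after surgery) | Status | Rule met | Exposure (days) | Late patient? |
|---|---|---|---|---|---|
| Perceval | 20 | alive | 1 | 21 | no |
| Perceval | 200 | alive | 1 | 201 | yes |
| Control | 20 | alive | none | undefined | undefined |
| Control | 200 | alive | none | undefined | undefined |
| Perceval | 20 | died later | 1 and 2 | 21 if rule 1 ranks first, otherwise 401 | no, otherwise yes |
| Control | 20 | died later | 2 | 401 | yes |
| Either | none | alive or dead | 3 or 2 | 401 | yes |

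Without explant the arms agree. With explant they do not. For a Perceval patient who is explanted and later dies, two rules apply and no precedence is stated.

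**Step 2: which outputs use this date.**

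- Extent of exposure: yes.
- Late patients, hence the crude late incidence rate: yes.
- Late patient-years, the denominator of the linearized late rates: no. They use study length, which runs to the last study date. That date has only death and alive rules and ignores explant. In the example they are (401 − 30)/365.25 = 1.016 years in every row.
- Time-to-event summaries: no. They follow SAP 5.2.
- Primary MACCE analysis: no.

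**Step 3: size if living explanted controls drop out of the denominator.** Let *f* be the fraction of controls explanted and alive, and 10.0% an illustrative true late rate. The reported rate is 10.0%/(1 − *f*). With 1234/2 = 617 controls:

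| *f* | Source | Patients (617 × *f*) | Reported rate |
|---|---|---|---|
| 0.5% | assumed low end | 3.1 | 10.0/0.995 = 10.05% |
| 1.3% | 100 − 98.7, stented group of a matched study, Protocol 6.2 | 8.0 | 10.0/0.987 = 10.13% |
| 5.3% | 100 − 94.7, one-year reoperation in the Perceval pivotal trial, Protocol 6.2 | 32.7 | 10.0/0.947 = 10.56% |

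This formula already keeps these patients' late events in the numerator. If their events were removed too, at the same 10% rate, the result would be 10.0% × (1 − *f*)/(1 − *f*) = 10.0%. The whole shift therefore comes from keeping their events, and nothing further is to be added.

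**Step 4: size if they are placed in rule 3 instead.** Late status then differs between arms only for explants by day 30. The control explanted at 20 days has exposure 401 and is late; the Perceval patient has exposure 21 and is not. After an explant at 200 days both are late. Extent of exposure still differs for any explant (401 against 201 days in that case). The control denominator does not shrink; the Perceval one loses its early explants.

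**The case against.** The strongest defence is that this is a drafting slip with an obvious meaning. Rule 3 says not explanted without naming a device, so the three rules look intended to be exhaustive: explanted, dead, neither. SAP 8.7 also uses the abbreviation ID in a medication rule that must apply to both arms. Read that way, rule 1 means the study valve and the arm asymmetry disappears. This is a fair account of the likely intent. It does not remove the conflict with the SAP's own definition, and two programmers could still produce different tables. Nor does it touch the numerator mismatch, which would then apply to early explants in both arms.

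The second defence is that little rests on it. SAP 13 summarizes safety data descriptively, and no claim depends on the crude late rate. That stands.

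A third objection is that redefining late patients is a separate matter from arm symmetry. That is also right: correcting rule 1 alone makes the arms symmetric, and the redefinition answers the mismatch.

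A reader might infer that late-event denominators in general differ by arm, or that control rates are inflated in Perceval's favour. The documents support neither. Late patient-years treat both arms alike. The direction holds only if an undefined date is taken to mean not late, which the SAP does not say. Under the rule 3 reading, Perceval loses early explants from its own denominator, which works against Perceval.

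**Conclusion.** The point holds in limited form. Under the SAP's definitions, a living control patient with an explanted valve has no last exposure date. The consequence is confined to extent of exposure and the crude late incidence rate. In addition, where exposure stops at explant, patients explanted by day 30 can be in the numerator of that rate and not in its denominator.

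The effect is small: about 10.13% instead of 10.0% at *f* = 1.3%, and 10.05% to 10.56% over 0.5% to 5.3%, if all living explanted controls drop out. Its direction is not fixed by the text. These figures rest on three assumptions:

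- The true late rate of 10.0% is illustrative.
- Reoperation stands in for explant. It is an approximate upper proxy, since not every reoperation is an explant and some explanted patients die. The protocol gives no time horizon for the 98.7% figure.
- The 5.3% end comes from a Perceval cohort and serves only as a high bound for controls.

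In the as-treated safety population the asymmetry follows the arm. In the as-randomized mITT tables it follows the valve actually implanted, so crossovers blur it. This is a minor correction, worth making because it is so cheap.

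**What to change.** Three edits to SAP Table 8:

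1. In last exposure date, replace the investigational device with the study valve (Perceval or control).
2. State that explant takes precedence over death when both apply.
3. Define late patients from follow-up after surgery: last study date − surgery date + 1 > 30.

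Edits 1 and 2 give every patient with a study valve a single rule, the same in both arms. Edit 3 makes the numerator and denominator of the crude late incidence rate cover the same subjects; without it, edit 1 would extend the early-explant mismatch to controls. Late patient-years do not change.

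The cost is a few words in one table, with no new data and no effect on the primary analysis.

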18.12. DATA DERIVATIONS

Table 8 : Data derivation rules

Derived variable	Derivation algorithm
Consented subject	Yes if filled date of consent No, otherwise.
Enrolled subject	Yes if filled date of consent AND patient is not a failure to implant (termination reason= FAILURE TO MEET RANDOMIZATION CRITERIA) No, otherwise.
ITT subject	Yes if Randomization date not empty No, otherwise.
mITT subject	Yes if ITT and the valve is a study valve (as listed in CRF). In case of "other" values, they have to be checked one by one with PM. No, otherwise.
Adherence to Randomization allocation	Yes if "Was the randomized valve implanted?" at first attempt=Yes No, otherwise.
SAF subject	Yes if Randomization and Implant dates not empty No, otherwise.
PP subject	Yes if 
 - Randomization and Implant dates not empty - Adherent to randomization - no major protocol violation (as reported in CRF field). No, otherwise.

Derived variable	Derivation algorithm
Operating room suite time (min)	Implant, Surgical time: Finish time – Start time
Skin-to-skin time (min)	Implant, Surgical time: Finish time – Start time
Extracorporeal circulation time (min)	Implant, Surgical time: Finish time – Start time
Cross clamp time (min)	Implant, Surgical time: Finish time – Start time
ICU stay (minutes)	Intensive Care Unit: [Date/Time of ICU Discharge] - [Date/Time of ICU Admission] If time of ICU discharge is missing it will be set at 23:59 If time of ICU Admission is missing it will be set at 00:00
ICU stay (days)	ICU stay (minutes) / 1440
Time to SAE	Serious Adverse Event (SAE): SAE start date – Surgery date +1
Early, Late SAE	EARLY if Time to SAE ≤ 30 days LATE if Time to SAE > 30 days

Derived variable	Derivation algorithm
Early safety (at 30 days)	
Serious Adverse Event (SAE):
 
YES if at least one (Time to SAE <=30 days) per CEC:
 
 - All-cause mortality - All stroke disabling and nondisabling - Life-threatening bleeding - Acute kidney injury—Stage 2 or 3 (including renal replacement therapy) - Coronary artery obstruction requiring intervention - Major vascular complication - Valve-related dysfunction requiring repeat procedure (BAV, TAVI, or SAVR): SVD and Aortic regurgitation requiring re-intervention 
NO, otherwise

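### SAP Table 8 starts late patient-years at enrolment but late events at surgery, so linearized late event rates come out slightly too low

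*SAP*

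**What the plan says.** SAP 13.1.2 plans linearized rates for all late serious adverse events under a constant-hazard model. One is the "total number of late events divided by the total time under evaluation after 30 days (late patient-years"); the other replaces the event count with the number of patients having at least one late event. SAP 18.12, Table 8, supplies the parts:

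- **Event clock.** Time to SAE is "SAE start date – Surgery date +1", and an event is "LATE if Time to SAE > 30 days".
- **Person-time clock.** Late patient-years are "Cumulative Study length (days) from 31st day/365.25". Study length is "Last study date – Enroll Date+1". Early patient-years are built from the same Study length, up to 30 days.
- **Late patients.** These are "Subjects with more than 30 FU days of exposure", and Extent of exposure is "Last exposure date-surgery date+1", so this row uses the surgery clock.

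Protocol 8.5.7 places randomization after enrolment and before the valve operation, so enrolment cannot follow surgery.

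**The concern.** A linearized rate is meaningful only if the time in the denominator is the time during which a counted event could occur. Here an event on postoperative day 20 is classed as early. For a subject enrolled 14 days before surgery, however, day 20 already contributes to late patient-years. The denominator holds time that cannot yield a late event, so the rate is pulled down. Table 8 is also inconsistent with itself, because late patients and late patient-years have different origins.

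What is at stake is the absolute level of the late complication rates per patient-year. These are descriptive safety results (SAP 13), but a reader may set them beside rates from other valve series, where a shifted time origin would not be visible.

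**Working it through.** The documents state no linearized rate and no patient-year total, so there is no plan figure to reproduce. The check is person-time arithmetic.

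**Inputs**
- Late boundary: 30 days (SAP 18.12).
- D, the last study day with surgery as day 1: 365 for the 1-year visit and 1826 for the 5-year visit (SAP 18.6, Table 7).
- g, the days from enrolment to surgery: not given in either document. Values of 7, 14 and 30 are assumptions.

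**Formulas, for a subject followed beyond day 30**
- Study length = D + g.
- Late days under the SAP rule = D + g - 30.
- Late days matching the event clock = D - 30.
- Understatement of the rate = 1 - (D - 30)/(D + g - 30) = g/(D + g - 30).

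**Where the extra days fall.** Day 31 of Study length is postoperative day 31 - g. For g up to 30, the extra g days are the last g days of the early postoperative period. For g above 30, preoperative days are included as well.

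**Results**

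| Follow-up | g = 7 | g = 14 | g = 30 |
|---|---|---|---|
| D = 365 (335 matched late days) | 7/342 = 2.0% | 14/349 = 4.0% | 30/365 = 8.2% |
| D = 1826 (1796 matched late days) | 7/1803 = 0.4% | 14/1810 = 0.8% | 30/1826 = 1.6% |

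As an illustration, a rate of 2.00 per 100 patient-years would be reported at D = 365 as 2.00 × 335/349 = 1.92 (g = 14) or 2.00 × 335/365 = 1.84 (g = 30).

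**If follow-up beyond 1 year is used at the primary analysis.** Protocol 8.6.1 expects about 30 months of accrual, and protocol 8.1 places the primary analysis 12 months after accrual ends. Assuming uniform accrual and no truncation, follow-up runs from 12 to 42 months with a mean of 27. That is 27 × 30.4375 = 822 days, or 792 matched late days. The understatement is then 7/799 = 0.9%, 14/806 = 1.7% or 30/822 = 3.6%.

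**Early patient-years.** For anyone followed beyond day 30 the total is 30 days on either clock, although the SAP rule fills part of it with preoperative days. The total changes only for subjects with shorter follow-up. As a check on that group, take a subject enrolled 40 days before surgery who dies on postoperative day 5. Study length is 45 days, so the late row would credit 15 late days to someone with none, unless its exclusion of subjects with under 31 follow-up days is read on the surgery clock.

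**The case against.** **The 31st day might mean Study Day 31.** SAP 5.4 makes the day of implant Day 1, and SAP 13.1.2 speaks of the post-implant period from Day 1. On that reading the gap disappears. But the row names Study length, and Table 8 gives that variable the enrolment date as its origin. If the surgery clock was intended, the row still needs correcting, since two programmers could produce different denominators.

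**The impact is small.** This stands. Safety is descriptive, and no test is planned on these rates. Both arms use the same rule and randomization follows enrolment, so the gap should be similar in the two arms. SAP 13.1.2 also plans time-to-event summaries for deaths, explants and the main cardiovascular events, with onset counted from implant (SAP 18.10.3). Protocol 8.7.1 places CT, echocardiography and eligibility review before inclusion, so the gap need not contain that work-up and may be short.

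**A reader might infer that post-explant time also lowers every late rate.** Last study date has no explant stop, whereas Last exposure date does: "For explant of investigational device: date of explant". But Time to SAE has no explant cut-off either. A stroke or bleed after explant stays in the numerator, and its person-time belongs in the denominator. A mismatch could arise only for events that need the study valve in place, such as structural deterioration or valve thrombosis. Protocol 18.1 lists explant as an end-of-trial event with follow-up required at least to 1 year, so such time may be limited.

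**A reader might also infer that Extent of exposure is the ready-made denominator.** As worded it is not. It would leave post-explant events without person-time. Its explant stop names only the investigational device, which SAP 5.4 describes as Perceval, and an explanted control patient who is alive fits none of the listed cases. The arms could then be treated differently, which the present rule does not do.

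**Conclusion.** The inconsistency is real on the literal text: late events and late patients use the surgery clock, while late patient-years use the enrolment clock. Whenever enrolment precedes surgery by at least a day, the enrolment part of the error can only lower the linearized rates.

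Its size rests on a gap that the documents do not give. It is zero for same-day surgery and falls as follow-up lengthens. At the assumed gaps it is a few percent of the rate at one year and under 2% at five years.

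The documents do not support reading this as a bias in the comparison between arms, as a threat to the primary endpoint, or as a general understatement due to explant. It is a low-impact error in a stated derivation rule, and it is inexpensive to correct before the tables are programmed.

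**What to change.** In SAP 18.12, Table 8, for all subjects in both arms:

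- Late patient-years = sum of max(0, Last study date - Surgery date + 1 - 30)/365.25.
- Early patient-years = sum of min(Last study date - Surgery date + 1, 30)/365.25.

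The total Patient-years row also uses Study length. After the change it will exceed early plus late time by the enrolment-to-surgery gap, so either re-anchor it to surgery or footnote the difference.

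For events that need the study valve in place, state whether time stops at explant. If it does, apply the same stop to both arms and to both numerator and denominator. Do not substitute Extent of exposure as it now stands.

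The cost is two derivation lines and a short explant rule. The surgery date is already used for Time to SAE, so no new data are needed.

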18.10. HANDLING OF MISSING DATES

The term missing date refers to a completely missing date or to an incomplete date where parts are not available. If the number of AE with missing date information does not exceed 5% the following imputation strategy is applied.

Missing start and stop date will be imputed conservatively, i.e., missing values will be imputed in such a way that the duration of the AE is considered with the longest possible duration and such that, whenever the AE may potentially start after implantation, the AE will be handled as a TEAE. Further information are reported in Section 18.12 (AE start date) and Figure 3 (AE stop date).

A replacement of missing year for AE start information is not foreseen. If needed, this will be considered on a case-by-case decision which must be documented together with the documentation of ADaM data sets.

Figure 3: Graphical overview about the imputation strategy

I1-I4: imputation steps
C1-C4: checkpoints

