Clinical efficacy (after 30 days)	
Serious Adverse Event (SAE):
 
YES if at least one (Time to SAE >30 days) per CEC or Echo core lab:
 
 - All-cause mortality - All stroke (disabling and nondisabling) - Requiring hospitalizations for valve-related symptoms or worsening congestive heart failure. - NYHA class III or IV (date of assessment >30 days after valve implant) - Valve-related dysfunction: 
 i. (mean aortic valve gradient ≥ 20 mm Hg, EOA ≤ 0.9–1.1 cm² and/or DVI < 0.35 m/s, AND/OR ii. moderate or severe prosthetic valve regurgitation) 
NO, otherwise

Derived variable	Derivation algorithm
Time-related valve safety	
Serious Adverse Event (SAE):
 
YES if at least one (Time to SAE >30 days) per CEC or echo core lab:
 
 - Structural valve deterioration (both points i. and ii. have to be met): 
 i. Valve-related dysfunction: 
 ▪ mean aortic valve gradient ≥ 20 mm Hg, EOA ≤ 0.9(if BSA<1.6 cm²) or 1.1(if BSA≥ 1.6 cm²) cm² and/or DVI<0.35 m/s, AND/OR ▪ moderate or severe prosthetic valve regurgitation) ii. Requiring repeat procedure (TAVI or SAVR) - Prosthetic valve endocarditis - Prosthetic valve thrombosis - Thrombo-embolic event, non-cerebral , - TIA - STROKE - VARC bleeding (BARC type 5, BARC type 3A, 3B and 3C, BARC type 2), unless clearly unrelated to valve therapy (e.g., trauma) : Device and/or procedure related 
NO, otherwise

MACCE (Yes/No)	
Serious Adverse Event (SAE), Valve re-intervention:
 
YES if at least one per CEC:
 
 - Death - Myocardial infarction - Stroke - Reintervention 
NO, otherwise

Derived variable	Derivation algorithm
MACCE @ 1 year (Yes/No)	
Serious Adverse Event (SAE), Valve re-intervention:
 
YES if at least one per CEC:
 
 - Death (Time to SAE <=365 days) - Myocardial infarction (Time to SAE <=365 days) per CEC - Stroke (Time to SAE <=365 days) per CEC - Reintervention (Time to SAE <=365 days) 
NO, otherwise

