SAE starting date (missing)	In case of missing SAE starting date, the following rule will be applied: 
 1. If missing day: 1st day of the month 2. If missing day and month: 01-JAN 3. If totally missing: Date of surgery SAE starting date cannot be before the surgery date. In that case, SAE starting date will be set as date of surgery.
Deaths	Death is when there is a SAE: 
 - With outcome='FATAL' OR - Leading to death (SAE criteria) The date of death is retrieved from the SAE form (Date of death).
Leak severity	Leak will be classified in: 
 1. none/trace: if "Is there a Paravalvular Leak?" ("Is there a Central Leak?")='No' or severity=' Trace (<1/4+)' 2. mild: if severity=' Mild (1/4+)' 3. moderate/severe: if severity=' Moderate (2/4+)' or severity=' Severe (>= 3/4+)'

Derived variable	Derivation algorithm
Proportion of patient event-free at one year	For each MACCE component: Numerator: #patients who experienced the specific MACCE component within DAY 365 Denominator: #patients who experienced the specific MACCE component within DAY 365 + # patients without the specific event at DAY 365
Proportion of patient MACCE-free at each year	Numerator: #patients who experienced MACCE within DAY 365 (730, 1095, 1460, 1825) Denominator: #patients who experienced MACCE within DAY 365 (730, 1095, 1460, 1825) + # patients without MACCE at DAY 365 (730, 1095, 1460, 1825)
MPG Gradient class	Aortic Mean Pressure Gradient (MPG) class: 
 • MPG \geq 20mmHG • MPG < 20mmHG
Hospitalization time [days]	Discharge – Hospital Admission +1
Ward time [days]	Hospitalization time – ICU time
EQ-VAS	Use as first source of values the “EQ5D02-Your Health Today” variable. If it’s missing, use the “EQ VAS Score” to replace the missing value.
Aortic Mean Pressure Gradient (MPG) with LVOT adjustment	Aortic Mean Pressure Gradient - LVOT Mean Pressure Gradient
Peak Mean Pressure Gradient (MPG) with LVOT adjustment	Aortic Peak Pressure Gradient - LVOT Peak Pressure Gradient

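### SAP Table 8 dates a wholly undated SAE to the day of surgery, which conflicts with SAP 18.10 and turns late events into day-1 events in the one-year and 30-day endpoints

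*SAP*

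**What the plan says.** SAP 18.12, Table 8, gives three rules for an incomplete SAE start date: "If missing day: 1st day of the month"; "If missing day and month: 01-JAN"; and "If totally missing: Date of surgery". It adds a floor: "SAE starting date cannot be before the surgery date". Time to SAE is the start date minus the surgery date plus 1.

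That variable feeds several derivations in the same table:
- the one-year primary endpoint, for example "Stroke (Time to SAE <=365 days) per CEC";
- the early/late split, "EARLY if Time to SAE ≤ 30 days", and the 30-day safety composite;
- the clinical-efficacy and time-related valve-safety composites, which count only events after day 30.

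SAP 18.10 states the general principle that "missing values will be imputed in such a way that the duration of the AE is considered with the longest possible duration" and sends the reader to 18.12 for start dates. It makes one exception, for a missing year: "A replacement of missing year for AE start information is not foreseen". If replacement is needed, it is to be decided and documented case by case. The strategy as a whole is conditional on AEs with missing date information not exceeding 5%. Table 8 carries neither the exception nor the condition.

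**The concern.** There are two separate problems.

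The first is a conflict. When the date is wholly missing, so is the year. Section 18.10 then calls for an individual decision, while Table 8 fills in the surgery date automatically. Two programmers, each following one of these sections, could give the same patient different one-year MACCE flags. The SAP change history shows that version 5.0 revised both sections, and the current texts still differ.

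The second is what the default does. The reasons 18.10 gives for early imputation are the longest AE duration and capture of treatment-emergent events. Neither bears on whether an event falls inside a 30-day or 365-day window. Late events will be in the database at the primary analysis, because accrual runs about 30 months and SAP section 11 expects follow-up beyond one year. A wholly undated late event enters the one-year endpoint, the 30-day composite and the 72-hour summary, and drops out of the late tables. Table 8 does not use visits at which the subject was recorded free of the event.

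**Working it through.** **1. Where the two sections agree and differ**

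| Missing part | SAP 18.10 | SAP Table 8 | Conflict? |
|---|---|---|---|
| Day | earliest start (longest duration); detail left to 18.12 | 1st of the month | no |
| Day and month | same | 1 January | no |
| Whole date | year not replaced; case by case | surgery date | yes |
| Limit on use | AEs with missing dates not above 5% | none stated | yes |

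**2. Which events can cross a cut-off**

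Imputed date = the later of (Table 8 date, surgery date). Time to SAE = imputed date − surgery date + 1. This was applied to every surgery day from 2016 to 2018 (an assumed calendar), with true event days spread evenly over each window.

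| Missing | Cut-off | True days that can cross | Share of that window that crosses |
|---|---|---|---|
| Day | 30 | 31–60 | 49% |
| Day | 365 | 366–395 | 49% |
| Day and month | 30 | 31–394 | 50% |
| Day and month | 365 | 366–729 | 50% |
| Whole date | both | any later day | 100% |

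The last row needs no simulation: surgery date − surgery date + 1 = 1.

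Examples:
- Surgery 15 March 2017, event 20 April 2017 (day 37), day missing: imputed 1 April, day 18. It becomes a 30-day event.
- Surgery 15 June 2017, event 1 October 2018 (day 474), day and month missing: imputed 1 January 2018, day 201. It becomes a one-year event.
- Surgery 15 June 2017, event 1 March 2019 (day 625), day and month missing: imputed 1 January 2019, day 566. It does not cross.

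**3. Weight of one patient**

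With the protocol's 10% attrition, per-protocol numbers per arm are 900 × 0.9 / 2 = 405 to 1234 × 0.9 / 2 = 555. One reclassified patient moves an arm's one-year rate by 100/555 = 0.18 to 100/405 = 0.25 percentage points.

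**4. Effect on the primary result**

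First, the plan's own power figures. The normal approximation is power = Φ(0.05 / √(2p(1−p)/n) − z), with n = 555.3 per arm (maximum sample size, interim looks ignored) and z = 2.005 for the 0.9775 threshold.
- p = 0.91: standard error 0.01717, Φ(2.911 − 2.005) = 0.818; the plan gives 0.805.
- p = 0.88: standard error 0.01950, Φ(2.564 − 2.005) = 0.712; the plan gives 0.704.

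Both are close enough to judge a shift.

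Next, inputs that the documents do not give, so assumed: a MACCE hazard after year 1 of 2% to 8% per year, equal in both arms, and 1% or 5% of late MACCE dates wholly missing. Mean follow-up beyond day 365 is taken as half of 30 months, or 1.25 years.

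Added one-year MACCE = 0.91 × 1.25 × hazard × share missing.

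| Hazard per year | Share missing | Added one-year MACCE (points) | Approximate power (0.818 without) |
|---|---|---|---|
| 2% | 1% | 0.02 | 0.817 |
| 8% | 1% | 0.09 | 0.814 |
| 2% | 5% | 0.11 | 0.813 |
| 8% | 5% | 0.46 | 0.800 |

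**The case against.** The strongest reply is that the rule will rarely matter. The protocol requires SAEs to be reported within 3 calendar days of awareness with source documents, data are queried and source-verified, and strokes and infarctions are adjudicated. A wholly undated MACCE would be unusual. The 5% in 18.10 covers AEs with any missing date information, so the 5% case above is close to a worst case. This stands, and it is why the effect on the primary result is put as small. It does not remove a default that gives a known wrong answer whenever it is used.

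Three stronger readings are tempting, and the documents do not support them.
- A reader might infer that all of Table 8's date imputation contradicts 18.10. It does not. For partial dates Table 8 carries out the longest-duration principle, and 18.10 points to it.
- A reader might infer that late events in general become one-year events. With a partial date, nothing beyond day 395 (day missing) or day 729 (day and month missing) can cross day 365. A year-3 stroke is pulled in only if its date is wholly missing.
- A reader might infer that the rule favours the Perceval valve in the non-inferiority test. The rule is the same in both arms. With equal late hazards it lowers power slightly, and with a higher Perceval late rate it works against Perceval. It would help Perceval only if controls had more undated late events, and nothing in the documents suggests that.

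Some components also have other dates. Table 8 takes death from a date-of-death field and times pacemakers by implant date. One-year MACCE, including death, is nevertheless written in terms of Time to SAE, so which date governs is unclear. Figure 3 of 18.10 is not available to this review. The text ties it to stop dates, but it may contain checks not seen here.

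**Conclusion.** The point holds in a limited form. Table 8 and 18.10 conflict on a missing year and on the 5% condition. The surgery-date default turns every wholly undated late stroke, infarction or re-intervention SAE into a day-1 event, whatever later visits show. Partial-date imputation is consistent with 18.10, but about half of the incompletely dated events in the windows above cross a cut-off.

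The likely effect on the primary result is small: 0.02 to 0.46 percentage points on one-year MACCE, and approximate power between 0.817 and 0.800 against 0.818. These figures rest on the assumed late hazards, shares of missing dates and equal arms. The actual number of incomplete dates is not in the documents. The 30-day composite and the early/late tables are more exposed, because with day and month missing an event as late as day 394 can be counted as a 30-day event. The change is worth making before database lock.

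**What to change.** 1. Reconcile 18.10 and Table 8 on the missing year, and state in both whether the 5% condition applies and what happens if it is exceeded.
2. Remove the surgery-date default. Set every imputed SAE start date no earlier than the day after the last contact at which the subject was recorded free of that event, and no later than the first record of the event. Within those bounds keep the earliest date, in line with 18.10. This also gives a fixed rule for wholly missing dates, which is preferable to ad hoc decisions in an unblinded trial analysed by the sponsor.
3. State which date governs MACCE timing for each component: SAE start, date of death, re-intervention date, or a date assigned by the Clinical Events Committee. The last applies only if the committee assigns one, which the protocol and SAP do not say.
4. Add a sensitivity run of one-year MACCE and the 30-day composites using the latest plausible date within the same bounds, and report how many dates were imputed in each arm.

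The cost is SAP wording and a few lines of code. Visit and reporting dates are already collected. The downside is one small extra analysis.
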